Title of the study:

Impact of renal replacement therapy modality on coagulation and platelet function in critically ill patients: Intermittent hemodialysis vs. continuous renal replacement therapy

The National Clinical Trial (NCT) number: NCT04512131

Date of the documenta: December 20, 2023

Study Protocol wih Statistical Analysis Plan (SAP)

Study Protocol

Study design and patients

This was a single-center prospective observational study. The institutional review board at Seoul National University Hospital approved the protocol (H-2007-102-1141). Patients or their surrogates provided written informed consent before enrollment.

Adult patients admitted to a surgical or medical intensive care unit (ICU) and were underwent a session of iHD or at least 48 hours of CRRT or both modalities between August 2020 and January 2023 were included. Patients were excluded if they fulfilled one of the following criteria: duration of CRRT was less than 48 hours, received platelet concentrates, fresh frozen plasma, or cryoprecipitate, discontinuation or initiation of the antiplatelet agents or anticoagulants during the study period, technical errors in laboratory tests.

Renal replacement therapy

All patients underwent either iHD or CRRT or both, according to the clinical situation. The detailed setting of RRT including blood flow rate, dialysis flow rate, ultrafiltration rate, duration, and use of anticoagulants was determined by nephrologists and intensivists. Patients were divided into the iHD or CRRT group according to the applied RRT modality. If both methods were applied to a patient, data from both modalities were included in the analysis. Each patient was exposed to a single episode of iHD or at least 48 hours of continuous venovenous hemodiafiltration or both. In the iHD group, hemodialysis was applied for 2 to 4 hours depending on the clinical condition of patients. Since maintenance iHD is usually performed 3 times a week, 48 hours of CRRT was deemed comparable to a single session of iHD.

Laboratory investigations

In the iHD group, blood samples were obtained immediately before and after the hemodialysis session. In the CRRT group, blood samples were taken within 24 hours of initiation of CRRT and the second samples were taken 48 hours after collection of the first samples.

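### The sampled iHD session and the order of the two modalities are not fixed, so the unadjusted iHD versus CRRT comparison cannot separate modality from earlier RRT

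*Combined protocol and SAP*

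**What the plan says.** The relevant text is in the Study Protocol, with the test in the SAP.

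- **Eligibility** (Study design and patients): adults who "underwent a session of iHD or at least 48 hours of CRRT or both modalities between August 2020 and January 2023 were included". The exclusions cover short CRRT, certain blood products, changes in antithrombotic drugs and laboratory errors. None concerns earlier RRT.
- **Choice of modality** (Renal replacement therapy): "All patients underwent either iHD or CRRT or both, according to the clinical situation".
- **Patients with both** (same section): "If both methods were applied to a patient, data from both modalities were included in the analysis". Exposure is described as follows: "Each patient was exposed to a single episode of iHD or at least 48 hours of continuous venovenous hemodiafiltration or both". Neither sentence gives a sequence or a gap.
- **Sampling** (Laboratory investigations): for iHD, "In the iHD group, blood samples were obtained immediately before and after the hemodialysis session". For CRRT, "In the CRRT group, blood samples were taken within 24 hours of initiation of CRRT and the second samples were taken 48 hours after" the first.
- **Outcomes** (Study outcomes): the primary outcome is the change in EXTEM CT. Changes are examined within each modality and then compared between the iHD and CRRT groups. Bleeding and transfusion over a 24-hour window are also compared between groups.
- **Test** (SAP): Student t-test or Mann-Whitney U for continuous data and chi-square for categorical data, with no covariates.

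**The concern.** CRRT has a defined starting point and iHD does not. An iHD record may be a patient's first RRT, a session after a period of CRRT, a repeat session, or one of many in a patient on maintenance dialysis. A CRRT record may likewise follow iHD. Because modality follows clinical need, the sequence in a patient who receives both is likely to track the course of the illness.

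The study's title question is the effect of modality. If the response to a session depends on earlier circuit exposure or stage of illness, and the groups differ in that history, the between-group difference mixes the two and the planned tests cannot separate them.

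This differs from the standard-error problem of counting a patient twice. A paired or mixed model that only allows for within-patient correlation corrects the variance and leaves an order effect in the estimate. Terms for order and interval are also needed.

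**Working it through.** **1. The plan's own figure.** Inputs from the SAP: SD 6.9 s, difference 5 s, two-sided 0.05, power 80%.

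n per group = 2 × (6.9 × (1.960 + 0.842) / 5)² = 29.9, so 30 per group and 60 in total. With 40% loss, 60 / 0.6 = 100. Both stated figures reproduce under a formula for two independent groups. The point does not depend on them; they supply the 5 s and 6.9 s used below.

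**2. The rules side by side.**

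| | iHD record | CRRT record |
|---|---|---|
| Baseline sample | just before a session; which session is not stated | some time in the first 24 h of CRRT |
| Second sample | just after the session (2-4 h) | 48 h after the baseline sample |
| Earlier RRT allowed | yes, no limit stated | yes, no limit stated |
| Minimum gap from the other modality | none stated | none stated |
| Adjustment for history | none | none |

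**3. What cancels and what does not.** Write a record's change as modality effect + h, where h is whatever the change owes to RRT history or stage of illness.

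- A stable offset in level is in both samples and drops out.
- A level that is still moving after recent RRT, or a response that depends on earlier exposure, stays in h.
- Bleeding and transfusion are counts of events with no baseline to subtract, so history enters those comparisons directly.

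**4. Illustration of size.** Let fI and fC be the shares of iHD and CRRT records that follow other RRT, and cI and cC the resulting shifts in CT change. Then

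bias in (iHD − CRRT) = fI·cI − fC·cC.

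The documents give none of these four quantities. If only one group is affected, with an assumed share of 0.1 to 0.5 and shift of 2.5 to 5 s, the bias runs from 0.1 × 2.5 = 0.25 s to 0.5 × 5 = 2.5 s, in either direction. It is zero if the shifts are nil or the two terms balance.

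Taking 6.9 s as the SD of the change (a further assumption, since the SAP gives it for the pre-dialysis level), SE = 6.9 × √(2/30) = 1.78 s at 30 per group and 6.9 × √(2/50) = 1.38 s at 50.

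Example: share 0.2, shift 5 s, bias 1 s, 30 per group.

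- False-positive rate with no true difference: Φ(1/1.78 − 1.96) + Φ(−1/1.78 − 1.96) = 8.7%.
- Power if the bias opposes a true 5 s: Φ(4/1.78 − 1.96) = 61%.

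| | 30 per group | 50 per group |
|---|---|---|
| False-positive rate, no bias | 5% | 5% |
| False-positive rate, bias 0.25 to 2.5 s | 5.2% to 28.9% | 5.4% to 44.1% |
| Power, no bias | 80% | 95% |
| Power, opposing bias 0.25 to 2.5 s | 76% to 29% | 93% to 44% |

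**5. Precision cost of a first-modality analysis.** With m iHD records removed from 30, SE = 6.9 × √(1/30 + 1/(30 − m)). For m = 5, 10 and 15, power for 5 s is 76%, 71% and 63%. Starting from 50 per group, it is 94%, 93% and 91%.

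**The case against.** A reader might infer more than the documents support.

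- **That an unexposed CRRT baseline is set against an exposed iHD baseline.** The CRRT baseline may itself follow up to 24 hours on the circuit, and being near the start of CRRT does not make it the patient's first RRT.
- **That the iHD change does carry over from CRRT.** The sequence and number of patients with both modalities are not reported. iHD followed by CRRT is equally permitted and would put any carry-over in the other group.
- **That an iHD baseline taken after CRRT biases the primary outcome in itself.** That describes a level. The outcome is a change over a 2-4 hour session, so a stable level difference is subtracted. A recovery trend has little time to act in iHD; it has 48 hours in CRRT.
- **That the bias has a known size, such as 20-40% of the target.** Setting the shift to 5 s, the whole target difference, makes that percentage simply the assumed share of records.
- **That a first-modality analysis should replace the main comparison.** It drops the within-patient information in patients treated both ways, and first-iHD and first-CRRT patients still differ by indication.

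All five objections stand. They do not dispose of the point: the text is silent on session, order, interval and earlier RRT, the tests are unadjusted, non-stable effects do not cancel, and the event outcomes get no protection from change scores.

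**Conclusion.** The point holds as a limit on attribution. As written, the plan cannot separate a modality effect from an effect of earlier RRT, in either direction, for changes in laboratory values or for 24-hour bleeding and transfusion. Neither the size nor the sign of any bias can be derived from the documents. The 0.25-2.5 s illustration rests on assumed shares and shifts, on only one group being affected, and on 6.9 s as the SD of the change; zero is also possible. The within-modality before-and-after description is not the target of this point. The change should be made because it is cheap and bears on the title question. Confidence is medium, since the number of affected records may be small.

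**What to change.** Leave treatment and sampling as they are and add the following to the SAP.

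1. From the dialysis record, classify each analysed record as first RRT of the ICU stay, after the same modality, after the other modality, or chronic maintenance dialysis. Record the hours since any earlier RRT. Report the counts by group, including the number and order of patients who contribute twice.
2. Add a pre-specified iHD versus CRRT analysis of EXTEM CT change and of 24-hour bleeding and transfusion, limited to each patient's first recorded modality.
3. Add an analysis of all records that accounts for repeated patients, with terms for order and for earlier RRT and its interval.
4. State that a difference will be attributed to modality only if it is consistent across these analyses.

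Enrolment ended in January 2023 and the document is dated December 2023. If the between-group results have already been seen, the added analyses should be labelled as such.

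Cost: several fields taken from existing records and a little more analysis work. The first-modality analysis is less precise, by the amounts in step 5 if that many records drop out. The adjusted model may be weakly supported if few patients had both modalities. Confounding by indication remains after all of this and should be stated with the result.

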The primary study outcome was changes in CT of EXTEM after dialysis. Secondary outcomes included changes in other EXTEM and FIBTEM parameters, AUC of platelet aggregometry, platelet count, PT, aPTT, fibrinogen concentration, D-dimer concentration, the activity level of protein C and protein S, bleeding events, and transfusion requirements after dialysis. Laboratory test results were compared before and after the application of each dialysis modality. To identify differences in changes according to dialysis modality, a comparison of each study outcome was made between the iHD group and the CRRT group. Bleeding events and transfusion requirements within 24 hours after dialysis in the iHD group or within 24 hours after the second blood sample collection in the CRRT group were also compared between the two groups. The severity of bleeding events were graded

by the modified World Health Organization bleeding scale.

SAP

Based on a previous study regarding the reproducibility of ROTEM results, the mean (\pm standard deviation) CT of EXTEM was set as 55 ± 6.9 seconds before dialysis. An absolute difference of 5 seconds in CT after dialysis was deemed significant. With a two-sided type-I error of 0.05 and a power of 80%, the required sample size was calculated to be 60 patients. Considering a loss to follow-up of 40%, the sample size was increased to 50 patients in each group, resulting in a total sample size of 100 patients.

Normally distributed continuous data were described as means and standard deviation and non-normal distributed data were described as a median and interquartile range [25th–75th interquartile range]. The normality of continuous data was assessed through the Shapiro-Wilk test. Comparisons between groups were performed by using the Student t-test or the Mann-Whitney U test for the continuous variables normally or non-normally distributed, respectively. Categorical variables were reported as numbers and percentages. Categorical data were compared with a chi-square test. A P value less than 0.05 was considered statistically significant and statistical analysis was performed using IBM SPSS 27.0 (IBM Corp, Armonk, NY, USA).

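### Bleeding and transfusion are compared between non-randomised modality groups with no pre-RRT value and no new-or-worsened rule, so differences already present at entry can enter the modality comparison

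*Combined protocol and SAP*

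**What the plan says.** All places are in the combined protocol and SAP.

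- **Study outcomes, laboratory tests.** These have a within-patient comparison: "Laboratory test results were compared before and after the application of each dialysis modality".
- **Study outcomes, clinical events.** The list of secondary outcomes ends with "bleeding events, and transfusion requirements after dialysis". The detailed sentence defines one window: "Bleeding events and transfusion requirements within 24 hours after dialysis in the iHD group or within 24 hours after the second blood sample collection". The second of these start points is for CRRT patients. What the sentence describes is a comparison between the two groups.
- **Study outcomes, grading.** Severity is graded "by the modified World Health Organization bleeding scale". Nothing says whether bleeding that continues from before RRT is an event.
- **Renal replacement therapy.** Modality was not randomised: "All patients underwent either iHD or CRRT or both, according to the clinical situation".
- **Study design and patients.** The population is surgical and medical ICU patients. One exclusion concerns those who "received platelet concentrates, fresh frozen plasma, or cryoprecipitate". Red cells and active bleeding are not mentioned.
- **Laboratory investigations.** The iHD sample is taken immediately before the session. For CRRT, "In the CRRT group, blood samples were taken within 24 hours of initiation of CRRT".
- **SAP.** "Categorical data were compared with a chi-square test". Continuous variables get a Student t-test or Mann-Whitney U test. No covariate adjustment is described.

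**The concern.** The plan asks what each modality does to haemostasis. For laboratory measures each patient supplies a starting value, so a stable difference in starting level between the groups is removed from the change. For bleeding and transfusion nothing plays that role.

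A surgical patient at grade 2 before CRRT and still at grade 2 in the window could be recorded as a bleeding event on CRRT or not, depending on how the chart reader interprets the word event. Transfusion is more clear-cut. Units given in the window are a count, and a new-onset reading does not help, because a patient who was already being transfused simply continues to contribute units.

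Clinicians chose the modality, so equal bleeding or transfusion status at entry cannot be assumed. Bleeding and transfusion are also the only clinical event outcomes in the plan, and readers are likely to take them as its safety comparison.

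**Working it through.** **1. The plan's own figure.** The only sample-size calculation is for EXTEM clotting time (SD 6.9 s, difference 5 s, two-sided 0.05, power 80%):

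n per group = 2 × [6.9 × (1.960 + 0.842) / 5]² = 29.9, so 30 per group and 60 in total. Allowing for 40% loss, 30 / (1 − 0.40) = 50 per group and 100 in total.

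This reproduces the plan. It says nothing about bleeding or transfusion, but it supplies the group sizes used below: 50 as enrolled, 30 if the full loss occurs.

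**2. What each outcome type has.**

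| | Laboratory tests | Bleeding, transfusion |
|---|---|---|
| Value at the start | yes, first sample | none described |
| Value afterwards | yes, second sample | yes, one 24 h window |
| Rule separating old from new | change from first sample | none |
| Adjustment between groups | none | none |

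**3. Size if ongoing bleeding is counted (assumed rates; none are in the documents).** Take new bleeding at 6% in both groups, so no modality effect, and persistent prior bleeding at 10% in one group and 4% in the other, as non-overlapping categories.

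- Observed rates: 6% + 10% = 16% and 6% + 4% = 10%, a difference of 6 points.
- Exact chance that the uncorrected chi-square gives p < 0.05, summed over two independent binomials: 15.2% at 50 per group and 11.1% at 30 per group.
- One table with exactly those rates, 8/50 vs 5/50, has p = 0.37.

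**4. Range over other assumptions.** New bleeding 5% in both groups among patients not already bleeding; observed rate = b + (1 − b) × 0.05, where b is persistent prior bleeding.

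| Prior bleeding b | Observed rates | Rejects, 50 per group | Rejects, 30 per group |
|---|---|---|---|
| 5% vs 5% | 9.75% vs 9.75% | 5.0% | 5.4% |
| 10% vs 10% | 14.5% vs 14.5% | 5.5% | 5.3% |
| 5% vs 10% | 9.75% vs 14.5% | 11.7% | 9.2% |
| 5% vs 15% | 9.75% vs 19.25% | 28.5% | 18.4% |
| 5% vs 25% | 9.75% vs 28.75% | 70.3% | 47.0% |

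With equal prior bleeding the error rate stays near 5%. The cost is then dilution: with 4% prior bleeding and 6% new bleeding in both groups, 4 / (4 + 6) = 40% of the counted events did not arise after RRT began. A spurious modality difference in bleeding therefore needs two things: ongoing bleeding is counted, and it is unequal between groups.

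**5. Where a baseline can sit.** The first CRRT sample may come up to 24 h after initiation. A baseline of the 24 h before that sample could therefore lie wholly on CRRT, while the same rule for iHD lies before the session. Bleeding that began on CRRT before the sample would be treated as pre-existing in that group only. The baseline has to be anchored to the start of RRT.

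**The case against.** **The text does not say that ongoing bleeding is counted.** A reader might infer that every bleed already present is recorded as an event after dialysis. The documents do not support that. An event in a window can equally mean onset in that window, and the plan is silent. Only the statement that it may be counted stands. For transfused units this objection does not help.

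**The secondary-outcome list opens with changes, which could govern the whole list.** Grammatically it could. But no earlier window is defined from which a change in bleeding or transfusion could be formed, and the detailed sentence compares the groups on the later window only.

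**The exclusions may already remove bleeders.** In part. Receipt of platelets, plasma or cryoprecipitate, and starting or stopping antiplatelet agents or anticoagulants, may take out some active bleeders. The period to which the blood-product exclusion applies is unclear, and it covers neither red cells nor bleeding managed without those products.

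**This is ordinary confounding in an openly observational study.** True of the imbalance. But the starting value of the outcome itself is the most direct covariate, and the plan uses one for the laboratory outcomes.

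**The consequence is speculative.** A reader might infer that the plan will report a false safety difference. That is not shown. No rate or imbalance is documented, and under the 16% vs 10% illustration about 85% of studies would not reach p < 0.05. The point estimate would still carry the 6 points.

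**These are secondary outcomes and enrolment is over.** Both true. The first limits the weight of the point; the second means that any new definition is post hoc.

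**Conclusion.** The point holds as a gap in method for two secondary outcomes. As written, the plan compares bleeding and transfusion between clinically selected groups with no pre-RRT value, no new-or-worsened rule and no adjustment. Differences at entry would stay inside the modality comparison, most clearly for transfused units.

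Direction and size cannot be derived from the documents. The figure of about 15% false rejections at 50 per group (11% at 30) rests on assumed rates of 16% vs 10%, on ongoing bleeding being counted, and on independent groups. With equal prior bleeding there is no spurious difference, only dilution.

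The primary outcome, EXTEM clotting time, and its sample size are not affected. Label: cheap improvement.

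**What to change.** 1. From the chart, extract the modified WHO grade and the transfused units for the 24 h before RRT start in both groups. Start means the beginning of the iHD session or CRRT initiation, not the first blood sample.
2. Count as an event new bleeding, or a rise of at least one grade from that baseline.
3. Adjust the transfusion comparison for baseline units.
4. Report baseline bleeding and transfusion by group, and keep all-bleeding counts as descriptive.
5. Because enrolment ended in January 2023 and the document is dated December 2023, label the redefined outcome post hoc. If the charts cannot supply the baseline, state that the counts may include bleeding present before RRT, and do not attribute a difference to modality.

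Cost: one further 24 h chart period per patient, about 100 patients, and fewer counted events.

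One limitation remains. The CRRT window opens 48 h after the first sample, so 0 + 48 = 48 h to 24 + 48 = 72 h after initiation. The iHD window opens after a 2 to 4 h session. The time between baseline and window therefore still differs by modality and should be stated with the result.

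### The iHD–CRRT comparison of change in EXTEM CT is unadjusted, although modality followed clinical need and the change spans 2–4 h in one group and 48 h in the other

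*Combined protocol and SAP*

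**What the plan says.** All references are to the combined protocol and SAP.

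- **Design and aim.** The title announces the "Impact of renal replacement therapy modality on coagulation and platelet function in critically ill patients". Under Study design and patients: "This was a single-center prospective observational study".
- **Assignment.** Under Renal replacement therapy: "All patients underwent either iHD or CRRT or both, according to the clinical situation". Clinicians also set the duration of treatment and the use of anticoagulants. A patient given both modalities contributes data to both groups.
- **Exposure.** Same section: "In the iHD group, hemodialysis was applied for 2 to 4 hours depending on the clinical condition of patients". The CRRT group needs at least 48 h. The plan reasons that, as maintenance iHD is usually given three times a week, "48 hours of CRRT was deemed comparable to a single session of iHD".
- **Sampling.** Under Laboratory investigations: "In the iHD group, blood samples were obtained immediately before and after the hemodialysis session". For CRRT, "blood samples were taken within 24 hours of initiation of CRRT and the second samples were taken 48 hours after collection of the first samples".
- **Analysis.** Under Study outcomes, results are compared before and after each modality, and then "a comparison of each study outcome was made between the iHD group and the CRRT group". The between-group tests in the SAP are the Student t-test, the Mann-Whitney U test and the chi-square test. No covariate, stratification, matching, sensitivity analysis or limit on interpretation is named.
- **Exclusions.** Patients who received platelets, plasma or cryoprecipitate, or who started or stopped antithrombotic drugs during the study period, are excluded.

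**The concern.** Two things other than modality can move the between-group difference in change.

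The first is case mix. Patients put on CRRT because of their clinical situation may differ from iHD patients in severity, in the reason for treatment and in ongoing antithrombotic use. The exclusions act on changes in antithrombotic treatment and on some blood products. They do not balance these characteristics.

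The second is elapsed time. An iHD patient's change covers a few hours, and a CRRT patient's change covers two days of critical illness and other care. The two intervals do not overlap, so interval and modality are the same variable in the data.

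A smaller point is that patients in both groups are handled as if they were different people.

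At stake is what the main contrast means. The title speaks of impact and the stated aim is to find differences by modality, so a difference produced by case mix or by two days of illness could be reported as an effect of the modality. The planned before and after values would show a gap in starting CT. They would not show drift over 48 h or selection on severity.

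**Working it through.** **1. Which contrast was the study sized for?** Inputs from the SAP: difference 5 s, SD 6.9 s, two-sided 0.05, power 80%, 40% loss. Two independent groups:

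n per group = 2 × [6.9 × (1.960 + 0.842) / 5]² = 29.9, so 30 per group and 60 in total. Then 60 / (1 − 0.40) = 100.

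Both stated figures reproduce. The numbers match the unadjusted iHD–CRRT contrast, so this contrast is not incidental.

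**2. What does a non-modality difference do to that test?** Assume no modality effect and a shift of b seconds in one group's mean change. The 6.9 s in the SAP is the SD of pre-dialysis CT. The SD of change is 6.9 × √(2(1 − ρ)), which equals 6.9 s only if the correlation ρ between the two samples is 0.5. The documents give no ρ, so I show a range. The standard error is SD × √(2/n); at ρ = 0.5 and n = 30 it is 6.9 × √(2/30) = 1.78 s. Probability of p<0.05 (noncentral t):

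| n per group | b | ρ = 0.3 (SD 8.16) | ρ = 0.5 (SD 6.90) | ρ = 0.7 (SD 5.34) |
|---|---|---|---|---|
| 30 | 1 s | 7.5% | 8.6% | 11.0% |
| 30 | 2 s | 15.4% | 19.7% | 29.7% |
| 50 | 1 s | 9.3% | 11.1% | 15.3% |
| 50 | 2 s | 22.8% | 30.0% | 45.7% |

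More patients make a biased difference more often significant. The values of b are assumptions.

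**3. Can adjustment remove it?**

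*Interval.* Suppose CT drifts linearly by D s per 48 h in everyone. With a 3 h session, the false difference is D × (48 − 3)/48, which is 0.94 s for D = 1 and 2.34 s for D = 2.5. At 30 per group and ρ = 0.5 the raw test rejects in 8.1% and 25.3%. In simulation, adjusting for first-sample CT gives 9.2% and 31.5%. Adjustment does not help, because the drift is added to every CRRT patient whatever the starting value.

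*Case mix.* Suppose severity shifts the change by 2 s per SD and the groups differ by 0.5 or 1 SD. The raw bias is 2 × 0.5 = 1.0 s or 2 × 1 = 2.0 s. Adjusting for a score of reliability r leaves about (1 − r) of it: 0.2 or 0.4 s at r = 0.8, and 0.5 or 1.0 s at r = 0.5. Here a model helps, if severity was recorded.

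**4. Patients in both groups.** If k of 30 per group are shared and their two changes correlate at c, the true variance of the difference is (1 − kc/30) times the one the test assumes. With k = 10 the factor is 0.9 at c = +0.3 and 1.1 at c = −0.3, and the actual type I error is about 4% or 6%. The plan does not state k.

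**5. Price of adjustment.** If covariates explain a share R² of modality and none of the remaining outcome variance, the variance grows by 1/(1 − R²). At 30 evaluable per group (normal approximation), power for 5 s falls from 80% to 76%, 71%, 65% or 59% for R² = 0.1, 0.2, 0.3 or 0.4.

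**The case against.** The strongest reply is that the plan is open about all this. It calls itself observational, sets out both sampling schedules and gives a reason for the 48 h. A continuous therapy has no 2–4 h session, so part of the difference in duration belongs to the question. The within-modality before/after comparisons are not confounded by differences between the groups. Shared patients bring the same stable characteristics to both groups, which reduces case-mix imbalance. Caveats on causality may also appear in the report, which is not available here.

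Much of that stands. Duration is partly the exposure. But the reason given rests on treatment frequency, and it does not equalise the illness course over 2–4 h and over 48 h. The before/after comparisons are still open to drift. The observational label is not itself a limit on interpretation.

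Three stronger readings are tempting and should be resisted.

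- A reader might infer that the comparison is known to be biased by seconds, or in a known direction. The documents give no drift, severity effect, baseline gap or correlation, so the calculations show what is possible and not what is likely.
- A reader might infer that regression would repair the comparison. It cannot repair the interval, and no severity score is listed as collected.
- A reader might place the second CRRT sample at hour 48 to 72 of treatment. The text requires only at least 48 h of CRRT and does not say that it was still running at the second sample.

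**Conclusion.** The concern holds in a limited form. The design facts are in the text: modality by clinical situation, a 2–4 h against a 48 h interval, a first CRRT sample that may follow up to 24 h of treatment, shared patients, and unadjusted tests for independent samples only. Together they allow case mix or illness course to be read as a difference by modality.

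The size is unknown. The illustration of about 9% or 20% false rejection for a 1 or 2 s non-modality difference assumes 30 per group, an SD of change of 6.9 s and no modality effect. The judgement rests on the design facts and not on those percentages. The stated comparability of 48 h to one session and the exclusions reduce the problem without removing it. The shared-patient issue is minor and can move the error rate either way. The sample-size arithmetic is correct and is not in question. The sponsor should make the change, but the plan's within-modality comparisons do not depend on it.

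**What to change.** 1. **Define the contrast in the SAP and the report.** It is the change across one 2–4 h iHD session against the change over a 48 h sampling interval in patients on CRRT for at least 48 h, first sampled up to 24 h after initiation, in non-randomised patients. State that a difference will not be attributed to modality alone, because no covariate can separate interval from modality.
2. **Show the groups.** Tabulate first-sample CT and patient characteristics by group, and give the number of patients who are in both.
3. **Add a supportive model beside the raw test.** Fit a linear model of change in CT on modality, with patient as cluster and a 95% CI. Adjust for ICU type, pre-existing antithrombotic use and illness severity where recorded, and show it with and without first-sample CT. If severity was not recorded, say that the model does not address selection by clinical situation. Enrolment ended in January 2023 and the document is dated December 2023, so label the model post hoc if data had been seen.

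The cost is wording, one table and one regression, with no new patients or samples. First-sample CT is measured. ICU type and antithrombotic status bear on eligibility, but the documents do not list them as collected data. The downsides are some loss of precision, estimates that may disagree, residual confounding and a weaker conclusion.
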